13.5. Derived Efficacy Endpoints

13.5.1. GA Lesion Size

For all independent ophthalmic assessments (performed by DARC laboratory), which includes GA lesion size, if assessments by only two independent readers are available, then the median of the 2 readings will be used in the calculation of summary statistics. If assessments by three independent readers are available, then the median of the three readings will be used for the summary calculations.

In the case that the GA lesion size has an indeterminate boundary noted, then the lesion size for this indeterminate boundary will be used in all analyses of GA lesion size unless otherwise noted in the case that primary lesions size assessment for an individual reader is missing.

13.5.2. MNRead Reading Chart

13.5.2.1. Reading Speed

13.5.2.1.1. Without adjustment for reading inaccuracy

Any print size with “Not Done” will have the associated wpm marked as 0.

Reading speed (wpm) = 600 / (reading time in seconds)

If reading speed >300 wpm, reading speed = 300.

13.5.2.1.2. With adjustment for reading inaccuracy

Any print size with “Not Done” will have the associated wpm marked as 0.

Reading speed (wpm) = $60 (10 - \text{errors}) / (\text{reading time in seconds})$

If reading speed >300 wpm, reading speed = 300.

If 10 or more errors were made in a sentence (implying wpm<0), then the reading speed for that sentence can be assumed to be zero (wpm).

13.5.2.2. Maximum reading speed

Maximum reading speed will be calculated as the mean of the three highest nonzero reading speeds (or 2 or 1 if that is all that exists). For subjects having all wpm values = 0, the maximum reading speed will be set to 0, and for those same visits the critical print size will be set to missing. Reading speed will equal 0 wpm at each print size for which (time=0) or Not Done (indicating no words in the sentence could not be read or sentence was not attempted due to vision) is checked for that print size.

13.5.2.3. Critical Print Size

Critical print size will be calculated as the smallest print size which support reading speed at 80% of the maximum reading speed. If all wpm at all print sizes = 0 at a visit then that visit's critical print size will be missing. Print size will be adjusted for viewing distance as follows:

- MNRead Charts:
 - For all viewing distances:
 - Print size = Print size + correction, where correction = $\log_{10} [40 / (\text{viewing distance in cm})]$, rounded to two decimal places

Note: the CRFs for the MNRead charts have print sizes pre-filled for a 40 cm viewing distance, while the Radner charts have print sizes pre-filled for a 32 cm viewing distance.

13.5.2.4. Reading acuity

Reading acuity will be calculated at each visit as: $1.4 - (\# \text{ sentences read} \times 0.1) + (\# \text{ of words read incorrectly} \times 0.01)$. This variable will not be included in the CSR.

13.5.3. Radner Reading Chart

13.5.3.1. Reading Speed

13.5.3.1.1. Without adjustment for reading inaccuracy

Reading Speed (wpm) = $14 / (\text{time in seconds}) \times 60 = 840 / (\text{time in seconds})$

If reading speed >300 wpm, reading speed = 300.

13.5.3.1.2. With adjustment for reading inaccuracy

Reading Speed (wpm) = $(14 - \text{errors}) / (\text{time in seconds}) \times 60$

If 14 or more errors were made in a sentence (implying $wpm < 0$), then the reading speed for that sentence can be assumed to be zero (wpm).

If reading speed > 300 wpm, reading speed = 300.

13.5.3.2. Maximum Reading Speed

Maximum reading speed will be calculated as the mean of the three highest nonzero reading speeds (or 2 or 1 if that is all that exists). For subjects having all wpm values = 0, the maximum reading speed will be set to 0, and for those same visits the critical print size will be set to missing. Reading speed will equal 0 wpm at each print size for which (time=0) or Not Done (indicating no words in the sentence could not be read or sentence was not attempted due to vision) is checked for that print size.

13.5.3.3. Critical Print Size

Critical print size will be calculated as the smallest print size which support reading speed at 80% of the maximum reading speed. If all wpm at all print sizes = 0 at a visit then that visit's critical print size will be missing. Print size needs to be adjusted for viewing distance as follows:

- Radner Charts:
 - For viewing distance of 32 cm
 - No correction is needed.
 - For viewing distance of other than 32 cm:
 - $\text{Print size} = \text{Print size} - 0.1 + \text{correction}$, where $\text{correction} = \log_{10} [40 / (\text{viewing distance in cm})]$, rounded to two decimal places

Note: the CRFs for the MNRead charts have print sizes pre-filled for a 40 cm viewing distance, while the Radner charts have print sizes pre-filled for a 32 cm viewing distance.

13.5.3.4. Reading Acuity

Reading acuity will be calculated at each visit as: $1.4 - (\# \text{ sentences read} \times 0.1) + (\# \text{ of words read incorrectly} \times 0.01)$. This variable will not be included in the CSR.

13.5.4. Mean FRI Index Score and FRI Level

Follow Section 4.3.2 of FRI Index User Manual (Version 1.4).

SAS code for scoring FRI Index and FRI Level is available in Appendix C of FRI Index Under Manual (Version 1.4).

13.5.5. NL-BCVA and LL-BCVA

13.5.5.1. BCVA Letter Score

- If the 4-meter score is > 19 letters read correctly, the visual acuity score is the sum of total letters correctly read at 4 meters plus the addition of 30.
- If the 4-meter score is ≤ 19 letters read correctly, the visual acuity score is the sum of total letters read correctly at 4 meters and total letters read correctly at the 1-meter distance.

- If no letters are read correctly at either the 4-meter distance or the 1-meter distance, the visual acuity score is 0.

13.5.5.2. Conversion of BCVA Letter Score to Snellen Equivalent

Conversions between letter, logMAR, and Snellen visual acuity scores are available in Beck et al. (2003) and Holladay et al. (2004). Letter scores are converted to logMAR equivalents using the formula $\text{logMAR} = 1.7 - (.02)(\text{letter score})$. With this conversion, a 5-letter difference in visual acuity is equivalent to a difference of 0.1 logMAR and to one Snellen line. Conversion from logMAR to Snellen can be done after rounding logMAR values to one decimal place following Table 1 in Holladay et al. (2004).

13.5.6. Low Luminance Deficit

$\text{LLD} = \text{NL-BCVA} - \text{LL-BCVA}$

13.5.7. NEI VFQ-25 scores

Scoring VFQ-25 with or without optional item is a two-step process:

- First, original numeric values from the survey are re-coded following the scoring rules outlined in Table 2 of user's manual. All items are scored so that a high score represents better functioning. Each item is then converted to a 0 to 100 scale so that the lowest and highest possible scores are set at 0 and 100 points, respectively. In this format, scores represent the achieved percentage of the total possible score, e.g., a score of 50 represents 50% of the highest possible score.
- In step 2, items within each sub-scale are averaged together to create the 12 sub-scale scores, Table 3 of user's manual indicates which items contribute to each specific sub-scale. Items that are left blank (missing data) are not taken into account when calculating the scale scores. Sub-scales with at least one item answered can be used to generate a sub-scale score. Hence, scores represent the average for all items in the sub-scale that the respondent answered.

13.5.7.1. NEI VFQ-25 Distance Activity Subscale Score

Average of items 8, 9, and 14

13.5.7.2. NEI VFQ-25 Near Activity Subscale Score

Average of items 5, 6, and 7

13.5.7.3. NEI VFQ-25 Driving Subscale Score

For subjects who are currently driving at baseline only. Average of items 15c, 16, 16a

13.5.7.4. NEI VFQ-25 Composite Scores

To calculate an overall composite score for the VFQ-25, simply average the vision-targeted sub-scale scores, excluding the general health rating question.

13.5.8. NEI VFQ-39 Scores

For subjects responded to additional questions A1-A13, VFQ-39 subscale scores can be calculated using Table 4 of user's manual.

13.5.8.1. NEI VFQ-39 Distance Activity Subscale Score

Average of items 8, 9, 14, A6, A7, and A8

13.5.8.2. NEI VFQ-39 Near Activity Subscale Score

Average of items 5, 6, 7, A3, A4, and A5

13.5.8.3. NEI VFQ-39 Composite score

Calculated by simply averaging the vision related subscales, excluding the general health rating question.

13.6. Repeated or Unscheduled Assessments of Safety Parameters

If a subject has repeated assessments before the start of investigational product, then the results from the final assessment made prior to the start of investigational product will be used as baseline. If end-of-study assessments are repeated or unscheduled, the last post-baseline assessment will be used as the end of study assessment for generating descriptive statistics. However, all post-baseline assessments will be used for PCS value determination and all assessments will be presented in the data listings.

13.7. Handling of Missing, Unused, and Spurious Data

13.7.1. Missing Date of Investigational Product

When the date of the last dose of investigational product is missing for a subject in the Safety set, all efforts should be made to obtain the date from the investigator.

13.7.2. Missing Date Information for Prior or Concomitant Medications (Therapies/Procedures)

If either the start or stop date of medication is missing, the worst or most conservative case will be considered when assigning medications to categories. So, for a missing start date (where stop date is after date of first dose or missing) the date will be imputed as the date of first dose; for a missing stop date the date will be imputed as the last study date.

13.7.2.1. Incomplete Start Date

The following rules will be applied to impute the missing numerical fields. If the stop date is complete and the imputed start date is after the stop date, then the start date will be imputed using the stop date.

13.7.2.1.1. Missing Day and Month

If the year of the incomplete start date is the same as the year of the date of the first dose of investigational product, then the day and month of the date of the first dose of investigational product will be assigned to the missing fields.

If the year of the incomplete start date is before the year of the date of the first dose of investigational product, then December 31 will be assigned to the missing fields.

If the year of the incomplete start date is after the year of the date of the first dose of investigational product, then 01 January will be assigned to the missing fields.

13.7.2.1.2. Missing Month Only

The day will be treated as missing and both month and day will be replaced according to the above procedure.

13.7.2.1.3. Missing Day Only

If the month and year of the incomplete start date are the same as the month and year of the date of the first dose of investigational product, then the day of the date of the first dose of investigational product will be assigned to the missing day.

If either the year is before the year of the date of the first dose of investigational product or if both years are the same but the month is before the month of the date of the first dose of investigational product, then the last day of the month will be assigned to the missing day.

If either the year is after the year of the date of the first dose of investigational product or if both years are the same but the month is after the month of the date of the first dose of investigational product, then the first day of the month will be assigned to the missing day.

13.7.2.2. Incomplete Stop Date

The following rules will be applied to impute the missing numerical fields. If the imputed stop date is before the start date (imputed or non-imputed start date), then the imputed stop date will be equal to the start date.

13.7.2.2.1. Missing Day and Month

If the year of the incomplete stop date is the same as the year as of the last study date, then the day and month of the date of the last study date will be assigned to the missing fields.

If the year of the incomplete stop date is before the year of the last study date, then 31 December will be assigned to the missing fields.

If the year of the incomplete stop date is after the year of the last study date, then 01 January will be assigned to the missing fields.

13.7.2.2.2. Missing Month Only

The day will be treated as missing and both month and day will be replaced according to the above procedure.

13.7.2.2.3. Missing Day Only

If the month and year of the incomplete stop date are the same as the month and year of the last study date, then the day of the last study date will be assigned to the missing day

If either the year is before the year of the last study date or if both years are the same but the month is before the month of the last study date, then the last day of the month will be assigned to the missing day

If either the year is after the year of the last study date or if both years are the same but the month is after the month of the last study date, then the first day of the month will be assigned to the missing day.

13.7.3. Missing Date Information for Adverse Events

Events with missing or partial dates will be handled such that in the absence of contradictory information an AE is treatment emergent. So, for a missing start date (where stop date is after first dosing date or missing) the date will be imputed as the first dose date; for a missing stop date the date will be imputed as the last study date. If a partial date is recorded, the following convention will be used to assign the AE.

13.7.3.1. Incomplete Start Date

If a start date is missing the day information and month/year is the same as first dose date then use first dose date, else '01' will be used for the day; if a start date is missing the month and the year is the same as first dose date then use first dose date, else January will be used for the start month.

If AE end date is earlier than treatment start date (i.e., could be inferred by any combination of year/month/day), then any missing part of AE start date will be imputed based on the AE end date.

13.7.3.2. Incomplete Stop Date

If a stop date is missing the day information and month/year is same as last study date then use last study date, else last day of the given month will be used for the stop day; if a stop date is missing the month and year is the same as last study date then use last study date, else December will be used for the stop month.

13.7.4. Missing Severity Assessment for Adverse Events

If severity is missing for an AE starting prior to the date of the first dose of investigational product, then a severity of "Mild" will be assigned. If the severity is missing for an AE starting on or after the date of the first dose of investigational product, then a severity of "Severe" will be assigned. The imputed values for severity assessment will be used for incidence summaries, while the actual values will be used in data listings.

13.7.5. Missing Relationship to Investigational Product for Adverse Events

If the relationship to investigational product is missing for an AE starting on or after the date of the first dose of investigational product, a causality of "Related" to the investigational product will be assigned. The imputed values for relationship to double-blind investigational product will be used for incidence summaries, while both the actual and the imputed values will be presented in data listings.

13.7.6. Character Values of Clinical Laboratory Variables

If the reported value of a clinical laboratory variable cannot be used in a statistical analysis (e.g., a character string is reported for a numerical variable), the appropriately determined coded value will be used in the statistical analysis, several examples are shown in [Table 7](#) for an illustration purpose. The actual values as reported in the database will be presented in data listings.

Table 7: Examples for Coding of Special Character Values for Clinical Laboratory Variables

Clinical Laboratory Test	Possible Results (in SI units)	Coded Value for Analysis
Chemistry: Bilirubin, Total/Direct	<1.7	0.85
	<2	1
Urinalysis: Specific Gravity	≤1.005	0.5025
	>1.030	1.030
Urinalysis: Glucose	≥55	Positive
	≤0	Negative
Urinalysis: pH	≥8.0	8.0
Urinalysis: Protein	≥500	500
Other: FSH	<0.2	0.1

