2.2.5. Safety Endpoints

- Incidence and severity of ocular and systemic treatment-emergent adverse events.
- Incidence of ADA directed against pegcetacoplan peptide or PEG.
- Incidence of new active CNV in the study eye.
- Incidence of new onset of subclinical CNV in the study eye.
- Incidence of subjects who lost letters based on NL-BCVA categories (≥ 15 , $\geq 15 - < 30$, ≥ 30 ETDRS letters).
- Change/shift from baseline in clinical labs and incidence of abnormal lab values.
- Change from baseline in vital signs and incidence of abnormal vital sign results.
- Shift from baseline in ocular examination assessments including slit-lamp examination and indirect ophthalmoscopy.
- Change from baseline in Intra Ocular Pressure (IOP) and incidence of IOP above specified thresholds.
- Change/shift from baseline in ocular imaging assessments (including specular microscopy; select sites).

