7.2. Clinical Laboratory Data

All laboratory parameters collected at each center's local laboratory will be normalized by converting values in original units to values in SI units and classified as normal, low, or high based on normal ranges supplied by the local laboratories and upon employing standardization.

Observed and change from baseline clinical laboratory data (hematology, chemistry and urinalysis) will be summarized by treatment group and protocol specified time points for the following clinical laboratory variables.

Hematology	Hemoglobin, hematocrit, red blood cells (RBC), platelet count, white blood cell count (WBC)– total and differential.
Biochemistry	Aspartate transaminase, alanine transaminase, alkaline phosphatase, sodium, potassium, chloride, bicarbonate, blood urea nitrogen (BUN), bilirubin (total, direct and indirect), creatinine, creatine kinase, glucose, and albumin.
Urinalysis	Glucose, specific gravity, blood, ketones, protein, bilirubin, pH, urobilinogen, leukocyte esterase, and nitrite.

Clinical laboratory test values are potentially clinically significant (PCS) if they meet either the low or high PCS criteria listed in [Table 3](#). The number and percentage of subjects with baseline and/or post-baseline PCS values will be tabulated by treatment group and overall.

The percentages will be calculated relative to the number of subjects with available values for

each lab parameter in each treatment group at the analysis visit. The numerator is the total number of subjects with at least 1 PCS value at the analysis visit. A supportive listing of subjects with post-baseline PCS values will be provided including the subject number, site, baseline, and post-baseline values.

Table 3: Criteria for Potentially Clinically Significant Laboratory Tests

Parameter	SI Unit	Lower Limit	Higher Limit
Biochemistry			
Albumin	g/L	<25 g/L	
Alanine Aminotransferase (ALT)	U/L		≥3*ULN
Alkaline Phosphatase (ALP)	U/L		≥3*ULN
Aspartate Aminotransferase (AST)	U/L		≥3*ULN
Bilirubin, Direct	umol/L		>1.5*ULN
Bilirubin, Total	umol/L		>1.5*ULN
Bicarbonate	mmol/L	<LLN	
Blood Urea nitrogen	mmol/L		>2.5*ULN
Chloride	mmol/L	<90 mmol/L	>115mmol/L
Creatinine	umol/L		≥178.8 umol/L
Creatine kinases	U/L		≥3*ULN
Glucose	mmol/L	<3.05 mmol/L	≥8.88 mmol/L
Potassium	mmol/L	<3.5 mmol/L	>5.5 mmol/L
Sodium	mmol/L	<130 mmol/L	>150 mmol/L
Hematology			
Hemoglobin	g/L	<0.9*LLN	
Hematocrit	%	<0.9*LLN	
Platelet Count	10 ⁹ /L	<LLN	
Urinalysis			

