13. DATA HANDLING CONVENTIONS

13.1. General Data Reporting Conventions

Continuous variables will be summarized using the number of non-missing observations (n), mean, SD, median, quartile 1, quartile 3, minimum, and maximum. Geometric mean and CV will be included for PK parameters, where appropriate. Categorical variables will be summarized using frequencies and percentages. Unless stated otherwise, for all percentages, the number of subjects in the analysis population for the treatment group will be the denominator.

Unless otherwise specified, the estimated mean and median for a set of values should be printed out to 1 more decimal place than the original values, and standard deviations should be printed out to 2 more decimal places than the original values. The minimum and maximum should report the same number of decimal places as the original values. Percentages will be displayed with 1 decimal place; except percentages will not be presented when the count is zero and 100% will be presented as an integer.

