1.2.4. Sample Code for Maximum Reading Speed and Critical Print Size

Please see below regarding the uncorrected and corrected reading speed calculation, and Critical Print Size: Flag = 1 MNREAD , 2 = Radner .

```
if flag = 1 then do;
  if (time = 0 or notdone = 1) then urs = 0;
  /** "Not Done" indicates the print size was not attempted due to vision or
  that the sentence was attempted but could not be read **/
  else if time > 0 then urs = 600/time;
  if urs > 300 then urs = 300;
  /** Calculate Corrected Reading Speed **/
  if (time = 0 or numerr >= 10) or (notdone = 1) then crs = 0;
  else if numerr >= 0 and time > 0 then crs = 60*(10-numerr)/time;
  else if (numerr = 0 or time = 0) then crs = urs;
  if crs > 300 then crs = 300;
end;
if flag = 2 then do;
  if (time = 0 or notdone = 1) then urs = 0;
  else if time > 0 then urs = 840/time;
  if urs > 300 then urs = 300;
  if (time = 0 or numerr >= 14) or (notdone = 1) then crs = 0;
  else if numerr >= 0 and time > 0 then crs = 60*(14-numerr)/time;
  else if (numerr = 0 or time = 0) then crs = urs;
  if crs > 300 then crs = 300;
end;
```

Critical Print Size:

```
if flag = 1 and n(aval,dist) =2 and dist ne 40 then aval = aval +
round(log10(40/dist),.01); /** Apply correction for viewing distance ne 40
**/
if flag = 2 and n(aval,dist) =2 and dist not in (32 40) then aval = aval -
0.1 + round(log10(40/dist),.01);
```

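### Table 7 of the SAP codes urine specific gravity '≤1.005' as 0.5025, half the limit, which puts an implausible value into the descriptive laboratory summaries

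*SAP*

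**What the plan says.** **Specific gravity.** SAP 13.7.6 covers laboratory results that cannot be analysed as reported, such as a string in a numeric field. For these, "the appropriately determined coded value will be used in the statistical analysis", and Table 7 gives examples. Two of its rows concern urine specific gravity: '≤1.005' becomes 0.5025 and '>1.030' becomes 1.030. Listings are treated differently: "The actual values as reported in the database will be presented in data listings".

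The coded values have a destination. SAP 7.2 states: "Observed and change from baseline clinical laboratory data (hematology, chemistry and urinalysis) will be summarized by treatment group", and specific gravity is one of the urinalysis variables it names. SAP 13.1 fixes the statistics: "Continuous variables will be summarized using the number of non-missing observations (n), mean, SD, median, quartile 1, quartile 3, minimum, and maximum". SAP 2.2.5 lists as a safety endpoint: "Change/shift from baseline in clinical labs and incidence of abnormal lab values".

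**Radner charts.** SAP 13.5.3.3 leaves the print size alone at 32 cm. Under "For viewing distance of other than 32 cm" it subtracts 0.1 and adds log10(40/distance), rounded to two decimals. Its note explains that "the Radner charts have print sizes pre-filled for a 32 cm viewing distance". The example code in SAP 1.2.4 has a different condition: "if flag = 2 and n(aval,dist) =2 and dist not in (32 40) then aval = aval", followed by the same adjustment. That condition exempts 40 cm as well as 32 cm.

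**The concern.** Taking half the limit is a familiar convention for a result below a detection limit, because the unknown value lies between zero and the limit. Bilirubin and FSH fit that description. Specific gravity does not: it is a ratio of density to that of water, so a result at or below 1.005 still lies close to 1. A value of 0.5025 would mean urine about half as dense as water.

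Table 7 does not apply halving to its upper-limit rows. It keeps the limit for specific gravity '>1.030', pH '≥8.0' and protein '≥500'. One variable is therefore coded by two rules, and the lower one produces an impossible number. Anyone programming from the SAP has no other instruction for this string and would enter 0.5025.

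At stake is the credibility of a descriptive safety table. A few such records could make the urinalysis means, SDs and changes unreadable and lead a reader to doubt the neighbouring results.

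The Radner mismatch is of a different kind. Two places in the SAP give different values for critical print size read at 40 cm, and a programmer who copied the example would not follow the text.

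**Working it through.** **1. Reproducing the Table 7 figure**

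| Variable | Reported | Coded | Coded/limit |
|---|---|---|---|
| Bilirubin | <1.7 | 0.85 | 1/2 |
| Bilirubin | <2 | 1 | 1/2 |
| FSH | <0.2 | 0.1 | 1/2 |
| Specific gravity | ≤1.005 | 0.5025 | 1/2 |
| Specific gravity | >1.030 | 1.030 | 1 |
| pH | ≥8.0 | 8.0 | 1 |
| Protein | ≥500 | 500 | 1 |

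The figure reproduces exactly: 1.005/2 = 0.5025. No halving rule is written down, but every lower-limit row with a numeric code follows it.

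**2. Effect on one record, compared with coding at the limit**

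- Level: 0.5025 − 1.005 = −0.5025. The two specific gravity limits are 1.030 − 1.005 = 0.025 apart, so the error is 0.5025/0.025 ≈ 20 times that span.
- Change, baseline 1.015 and later '≤1.005': 0.5025 − 1.015 = −0.5125, instead of 1.005 − 1.015 = −0.010.
- Change, baseline '≤1.005' and later 1.015: 1.015 − 0.5025 = +0.5125, instead of +0.010.
- If both visits are '≤1.005', the error cancels in the change.

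**3. Effect on a summary for 200 subjects** (group size from SAP 3.4; the number k of affected records is assumed, since the documents give none)

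The mean falls by k × 0.5025/200:

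- k = 1: 0.0025
- k = 10: 0.0251
- k = 20: 0.0503

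Ten records therefore move the mean by the whole span between the two limits. For the SD, suppose the other 199 values were all 1.005. One coded record would then give 0.5025 × √(0.005 × 0.995) = 0.035, more than the 0.025 span. SAP 13.1 prints the minimum to the decimals of the reported values, here three, so it would appear as about 0.503. With k at most 20 of 200 (10%), these records sit at the low end under either coding, so the first quartile and median of observed values ordinarily stay where they are.

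**4. Potentially clinically significant (PCS) flag** (conditional)

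Table 3 sets the low limit at 0.9 × LLN. The LLN is not given.

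- 0.5025 is flagged if LLN > 0.5025/0.9 = 0.558.
- 1.005 is flagged only if LLN > 1.005/0.9 = 1.117.
- For an assumed LLN of 1.000 to 1.010, the limit is 0.900 to 0.909: 0.5025 is flagged and 1.005 is not.

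**5. Radner adjustment, text against example code**

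Text: 0 at 32 cm, otherwise −0.1 + log10(40/d) rounded to two decimals. Code: the same, but 0 at 40 cm too.

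| Distance d (cm) | Text | Code | log10(32/d) |
|---|---|---|---|
| 20 | +0.20 | +0.20 | 0.204 |
| 25 | +0.10 | +0.10 | 0.107 |
| 32 | 0.00 | 0.00 | 0.000 |
| 36 | −0.05 | −0.05 | −0.051 |
| 40 | −0.10 | 0.00 | −0.097 |
| 50 | −0.20 | −0.20 | −0.194 |

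The text tracks the exact shift from a 32 cm pre-fill at every distance. The code departs from it only at 40 cm, by +0.10. A subject tested at 40 cm throughout has the same change from baseline either way. For a move from 40 to 25 cm, the text adds 0.10 − (−0.10) = 0.20 to the change and the code adds 0.10 − 0.00 = 0.10.

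**The case against.** The division itself is correct, so this is a poor choice of convention and not a miscalculation. That is right.

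Table 7 is offered as illustration, and SAP 13.7.6 leaves room for a suitable value to be determined. That also stands, and a careful programmer might depart from the cell. But its column is headed as the value for analysis and the SAP offers no alternative for this string, so the example is what will most naturally be implemented.

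The reach is limited. The summaries are descriptive, the listings show what the laboratory reported, and SAP 7.2 plans shift tables for hematology and chemistry only. Robust statistics printed beside the mean would reveal the problem.

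Three stronger readings are tempting, and the documents do not support them:

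- **Spurious PCS flags will appear.** The SAP does not say that coded values feed the Table 3 criteria, and it gives no LLN. The flag result is conditional on both.
- **Many records are affected.** Nothing states how often '≤1.005' is reported.
- **The Radner line biases the comparison with sham.** SAP 1.2 labels the code as examples that may need changing to match the SAP, and the text in 13.5.3.3 is coherent and governs. Even if the line were run, constant distances cancel in the change, the model in SAP 6.4.3 includes chart type and is repeated by chart type, and SAP 6.5 plans no hypothesis test. The number of readings at 40 cm is not given. No bias in a treatment contrast is shown.

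**Conclusion.** The specific gravity example is wrong as written. The size per affected record is certain: −0.5025 in level, and up to the same amount in change from baseline. The size in any table depends on a frequency the documents do not give; the counts of 1, 10 and 20 in 200 are assumptions. The damage falls on the mean, SD, minimum and change in descriptive urinalysis summaries. The primary and key secondary endpoints, the type I error control and the power are untouched.

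The Radner discrepancy is real but is only a code-alignment note. It produces a wrong value, +0.10 at 40 cm, only if the example line is run unchanged, and then on a non-key secondary endpoint. Overall this is a minor point, worth correcting because correction is so easy.

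**What to change.** 1. In SAP Table 7, code specific gravity '≤1.005' as 1.005, matching the treatment of '>1.030'. The PCS question then falls away for any LLN up to 1.117.
2. In SAP 1.2.4, for the Radner branch, replace `dist not in (32 40)` with `dist ne 32`, so that the example agrees with 13.5.3.3. This changes nothing at the other distances checked.

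The cost is one table cell and one line of example code, best edited before outputs are produced. Any laboratory or critical print size program already written from either place needs a check.
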